2.1 Background Information and Relevant Literature

Fine particulate matter air pollution (PM \leq 2.5 μ m in diameter, PM_{2.5}) exposure is associated with increased blood pressure.^{1, 2} Proposed mechanisms include increases in inflammation and oxidative stress leading to increased sympathetic tone and impaired vasomotor regulation.^{3, 4} We have identified gene expression changes in inflammatory pathways in association with increased particulate matter

pollution.⁵ Additionally, downstream changes were shown in protein expression of TNF α and other inflammatory biomarkers.⁶⁻⁸ Controlled human exposure studies show that exposure to air pollution increases TNF α ;⁹ *in vivo* and *in vitro* studies demonstrate that TNF α promotes the vascular inflammation and remodeling linked with increases in blood pressure and the development of hypertension.¹⁰ Given this spectrum of evidence, these studies support a probable role for air pollution in increasing TNF α and the hypothesis that increases in TNF α may be related to increases in blood pressure with fine particulate matter air pollution exposure.

While it is clear that increases in PM_{2.5} exposure are associated with increases in inflammation, **evidence is less well-established that reducing PM_{2.5} exposure will reduce inflammation.** Natural experiments in Beijing during the 2008 Olympics showed that reductions in PM_{2.5} due to regulations for the event were associated with reductions in concentrations of circulating inflammatory biomarkers compared to the months immediately before and after.¹¹ There are also limited studies of reducing cardiovascular risk factors by decreasing particulate matter exposure with the use of HEPA filtration by portable air cleaners (PACs). For example, in a meta-analysis of the effect of PAC use on blood pressure, our group showed a significant reduction in systolic blood pressure by \approx 4 mm Hg over a median of 13.5 days of intervention versus sham.¹² More recently, we also showed by meta-analysis that residential PAC use by adults is associated with reductions in circulating concentrations of CRP (10 studies, total N=570) and IL-6 (9 studies, total N=379).¹³ In these studies, active PAC use was associated with statistically significant 7% lower CRP and 13% lower IL-6 vs. sham control. TNF α was lower by 2%; however, this biomarker had insufficient data to reach statistical significance (5 studies, N=215). Multiple biomarkers have data supporting their associations with air pollution exposure. For example, recent studies have shown that PM_{2.5} exposure was associated with significant changes in Angiopoietin-1, ICAM-1 and VCAM-1,¹⁴ and increased expression of CRP, IL-6, TNF α , endothelin-1, fibrinogen, p-selectin.⁶⁻⁸ PCSK9 is an important pharmacologic target that has been shown to increase in association with increased particulate matter exposure.¹⁵ Soluble platelet selectin (sP-selectin) has been shown to increase with PM exposure; a small trial of 29 adults showed that sP-selectin decreased with PAC use versus sham.¹⁶ BNP increases were shown in human exposure trials using diesel exhaust, with reductions in BNP when exhaust was filtered.¹⁷ The data from these studies support connections with exposure and biomarker outcomes, but there are limited data from few small studies describing associations with PAC use. Given the important role in cardiovascular disease, and data showing relationships with pollutant exposure, we will primarily evaluate changes in TNF α in association with PAC use versus sham; and also will explore associations with Angiopoietin-1, ICAM-1, VCAM-1, PCSK9, sP-selectin, and BNP and other panel biomarkers. **There is a dearth of data on how personal interventions to reduce air pollution exposure affect cardiometabolic biomarkers and how those may mediate relationships with cardiovascular risk factors such as hypertension.** To address this gap we have proposed a randomized, double-blind, sham-controlled pilot trial to evaluate the changes in inflammation over 4 weeks of PAC use.

2.2 Rationale

Because PAC use has been associated with decreases in concentrations of circulating CRP and IL-6, we hypothesize the following: (1) Among adults with hypertension recruited from an outpatient clinical setting, 4 weeks of continuous home PAC use, compared with sham PACs, will be associated with decreased concentrations of TNF α when measured before and after intervention; (2) Reductions in measured PM_{2.5} from PAC use will be associated with decreased concentrations of circulating TNF α .

2.3 Potential Risks & Benefits

2.3.1 Known Potential Risks

This is a minimal risk study, with no physical risks associated with the study design. Potential minimal risks are as follows:

(1) **Risk of PAC use:** In our published review of the effect of personal air cleaners (PACs) on blood pressure control, no risks were reported.¹² While it is possible that use of a PAC might disrupt sleep, it is unlikely. In fact, frequently PACs have been used to generate “white noise” associated with improved sleep latency and duration in a variety of settings.

(2) Risk of monitoring air pollution: There are no known risks to participants with monitoring the amount of air pollution exposure. At conclusion of the 3-month study, data on air pollution exposure will be provided to study participants. There is no risk to participants in ongoing air pollution exposure during this time interval.

(3) Risk of blood collection. There are minimal risks associated with a standardized venipuncture for blood collection. These risks include pain, discomfort and superficial bleeding or bruising. All participants in the clinical cohort will provide consent for standard blood collection, in which these minimal risks will be described. For participants in the clinical cohort, up to <15 mL (≈ 1 tablespoons and $\approx 3\%$ of a standard blood donation) of blood will be collected at the baseline visit and 4-week visit. The total amount of blood collected will be <30 mL for the main study. For participants opting into biospecimen storage, an additional ≈ 10 mL will be drawn at each visit for a total of <50 mL for the entire study. This presents minimal risk to study participants.

(4) Risk of monitoring home blood pressure and ambulatory blood pressure. There are no known direct risks to participants associated with the use of home blood pressure monitors or ambulatory monitors. These devices are routinely prescribed for self-monitoring and clinician-assisted decision making for hypertension. There is a potential risk of increased anxiety due to self-monitoring of blood pressure. Study coordinators will discuss any concerns regarding home blood pressure monitoring at video visit with study participants and will refer any concerns on recorded blood pressure values to participants' managing physician.

(5) Risk of discomfort with staff visualizing participants' homes during video visit for equipment setup

(6) Loss of time related to study participation: to minimize this risk, staff will schedule video visits at participants' preferred times, and coordinate 4-week intervention period to facilitate clinic visits at convenient times for participants.

2.3.2 Known Potential Benefits

This research will significantly advance our understanding of the relationship between PAC use and inflammation, and potentially with blood pressure health outcomes. Using a sham-controlled design, the proposed study will provide robust evidence to enhance the existing knowledge on this subject and inform future research questions.

Though individual study participants may experience the above mentioned direct potential risks through their participation in this study, study participants may also benefit from the study: study participants will receive and keep their own personal PAC and BP monitor, these may result in lasting improvements in participant health via continued air filtration or enhanced awareness of their BP. Participants will also receive a small remuneration for each blood draw.

3 Objectives and Purpose

3.1 Primary Objective

The primary objective of this research is to examine the effectiveness of PAC use in improving inflammation related to cardiovascular disease.

Specific Aim 1: To determine if 4 weeks of home air filtration with PACs compared to sham is associated with significant reductions in TNF α concentrations when measured before and after intervention.

Specific Aim 2: To determine if reductions in PM $_{2.5}$ as a continuous variable are associated with significant reductions TNF α concentrations over a four-week period.

Exploratory Aim 1: To explore associations between PAC use and concentrations of cardiometabolic biomarkers using a targeted proteomic panel, the Olink Explore 384 Cardiometabolic panel, measured before and after 4 weeks of intervention.

Exploratory Aim 2: To explore if changes in TNF α and other novel cardiometabolic biomarkers partially mediate the effects of PACs on home blood pressure.

4 Study Design and Endpoints

4.1 Description of Study Design

In this research, we will conduct a randomized, double-blind, sham-controlled pilot trial to study the effect of PAC use on the concentrations of circulating biomarkers of inflammation in outpatient adults within the NYU Langone Health system.

Aim 1: To determine if 4 weeks of home air filtration with PACs compared to sham is associated with significant reductions in TNF α concentrations when measured before and after intervention.

Data collection will begin Q2 2022 with a total of two time points 4 weeks apart, pre- and post-intervention. The study design utilizes purposeful selection of 74 adults with stable hypertension within the NYU Langone health system outpatient cohort. We will define stable hypertension as no medication changes in prior 30 days, systolic BP <160 mm Hg and either \geq 130 mm Hg without antihypertensive medications, or diagnosis of hypertension in medical records. Per guidelines, this range is considered safe to monitor without changes in antihypertensive medications. At the initial clinic visit, blood will be collected and stored for analysis. We will measure circulating concentrations of TNF α using the Olink Explore 384 Cardiometabolic panel for this *a priori* specified analysis; this panel will also measure the concentrations of other biomarkers that we will explore further in Exploratory Aims 1 and 2. The Olink analysis uses a Proximity Extension Assay that has been shown to have high specificity and accuracy to allow for assessment of changes in concentrations between repeated samples over time.^{18, 19}

We will randomize participants to receive PAC with either true or sham filtration (HEPA filter removed). Equipment will be shipped to participant homes or given to participant at clinical visit along with written instructions for setup and use. Active and sham PACs, and pollution monitors, will be positioned in the bedroom where each participant sleeps. We will video conference with participants for initial setup of equipment, though prior data suggests that written instructions alone are effective in aiding participants in this process. We will use a commercially available portable air cleaner with a “true HEPA” filter for the true arm. For the sham arm, the same model will be used with HEPA filter removed, and has identical appearance and sound. After enrollment and baseline blood draw, Home BP will be monitored using commercially available device with a paired data hub that transmits BP measurements to an online dashboard in real time. We will monitor participant adherence to PAC use with electricity consumption monitors. Participants will be scheduled for a clinic visit after 4 weeks of PAC use to return data hubs, electricity monitors and pollution monitors to the study team, and will undergo post-treatment blood draw. A second blood draw will be performed and blood will be stored for analysis. Participants will receive reimbursement after equipment is returned and second blood draw is complete. Participants randomized to sham PAC arm will receive HEPA filters to install and keep.

Aim 2: To determine if reductions in PM_{2.5} as a continuous variable are associated with significant reductions TNF α concentrations over a four-week period. For Aim 2, the design is identical to above; however in addition, we will collect PM_{2.5} data using commercially available PM sensors placed in the same bedroom as PAC. While it has been shown that PACs significantly lower indoor PM_{2.5} concentrations, these data will allow us to examine the effect of PM as a continuous variable in addition to the binary variable of PAC use (active versus sham). Commercially available PM monitors will record indoor PM_{2.5} concentrations using dual (backup) sensors, which store measurements on internal SD cards. Commercially available PM sensors have been well validated and use laser particle counters to count the number of particles at varying sizes with a sampling frequency of 2 minutes. PM monitors will be returned and data will be retrieved from SD cards at the post-intervention blood draw visit. These data will be measured for the entire cohort.

Exploratory Aim 1: To explore associations between PAC use and concentrations of cardiometabolic biomarkers using a targeted proteomic panel, the Olink Explore 384

Cardiometabolic panel, measured before and after 4 weeks of intervention. For this Aim, we will utilize additional data generated from the Olink panel. The Olink Explore Cardiometabolic panel is for research use only and will not be used toward FDA approval or diagnostic purposes. It will generate no clinically actionable results. The panel measures 369 protein biomarkers associated with cardiovascular and metabolic disease. This panel has been used to investigate cardiovascular disease treatment and prevention in various adult populations.^{18, 19} The pathways represented in the cardiometabolic panel include angiogenesis, cell activation, cell adhesion, coagulation, complement activation, extracellular matrix organization, response to hypoxia, and others. We will explore associations between PAC use (active vs. sham) and changes in circulating concentrations of Angiopoietin-1, ICAM-1, VCAM-1, PCSK9, sP-selectin, and BNP and other panel biomarkers. This Exploratory Aim will require no additional action on the part of participants.

Exploratory Aim 2: To explore if changes in TNF α and other novel cardiometabolic biomarkers partially mediate the effects of PACs on home blood pressure. For this Aim, participants will monitor blood pressure daily during the 4-week intervention period using commercially available BP monitor with a paired data hub that transmits BP measurements to an online dashboard in real time. Participants will receive written and verbal instructions for proper BP recording technique at the baseline visit. They will record two measurements in a seated position each morning and evening during the study periods. The outcome of interest will be the mean of two AM systolic blood pressure measures. We will perform mediation analysis to analyze the direct and indirect effects of changes in significant biomarkers and PM_{2.5} changes on AM systolic BP. Based on our own pilot study of the effect of PAC use on AM systolic BP, we anticipate up to 30% missing BP measurements. We surveyed our prior pilot cohort regarding reasons for missing measurements and the predominant reported reason was forgetting; participants noted that they would have liked daily reminders. We will offer participants the option to receive daily text message reminders to record BP. These have been reported to be effective in other studies of home BP as well.

4.2 Study Endpoints

4.2.1 Primary Study Endpoints

Aim 1 and Aim 2: The primary study endpoint will be % change in concentration of TNF α over the 4-week intervention period calculated as:

$$\frac{([post - intervention] - [pre - intervention])}{[pre - intervention]} * 100\%$$

Because the baseline biomarker concentration for an individual is compared to post-intervention irrespective of range, percent change is a useful metric to compare reported results across assays.

4.2.2 Exploratory Endpoints

Exploratory Aim 1: The endpoints for Exploratory Aim 1 will be the % change in concentration of biomarkers from the Olink Explore Cardiometabolic panel over the 4-week intervention period calculated as:

$$\frac{([post - intervention] - [pre - intervention])}{[pre - intervention]} * 100\%$$

Exploratory Aim 2: The endpoint for Exploratory Aim 2 will be the change in AM systolic BP (mm Hg) as a function of the change in PM_{2.5} (in $\mu\text{g}/\text{m}^3$) from baseline.

5 Study Enrollment and Withdrawal

5.1 Inclusion Criteria

To be eligible to participate in the pilot, individuals must meet all of the following criteria:

1. Participant is ≥ 18 years old
1. Participant and members of household are reported to be non-smokers (defined as no household members are currently known to smoke cigarettes or use other tobacco products including e-cigarettes)
2. Participant is to understand/speak English or Spanish
3. Participant can understand study procedures and give informed consent
4. Participant has stable hypertension: no medication changes in prior 30 days, systolic BP <160 mm Hg and either ≥ 130 mm Hg without antihypertensive medications, or diagnosis of hypertension in medical records
5. Able to measure home blood pressure twice daily
6. Able to participate in video conference for home equipment setup
7. Able to visit clinic for blood draws before and after the study period
8. Do not intend to sleep anywhere outside of primary bedroom for more than 48 consecutive hours or a total of 7 days during the study period.
9. Ability to lift, or access to assistance with lifting, 20 lb to set up PAC in bedroom.

5.2 Exclusion Criteria

Any individual who meets any of the following criteria will be excluded from participation in the pilot:

1. Participants who are unable to provide a minimum of at least one blood pressure measurement per day
2. Participants with average home blood pressure monitor readings of a systolic blood pressure (SBP) >160 mmHg over any 10-day period during the study. This will be considered evidence of uncontrolled hypertension and will require study termination.
3. Participants with known coronary artery disease
4. Participants with known systemic inflammatory conditions (such as rheumatoid arthritis, inflammatory bowel disease, cancer)
5. Participants currently taking any anti-inflammatory medications or medications that target inflammatory cytokines
6. Pregnancy
7. Participants with known or suspected Covid-19 in the prior 30 days
8. Participants with post-covid sequelae (a.k.a "Long covid")
9. Participants who are already utilizing HEPA filtration (PAC or within HVAC) in bedrooms

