5.4 Strategies for Recruitment and Retention

To achieve 44 study participants who complete the pilot, we will need to identify ≈ 300 eligible participants from the electronic health record (EHR) in NYU clinics and plan to enroll and randomize 44 participants. Utilizing support from DataCore and NYU Medical Center Information Technology, we will use SlicerDicer and other Epic tools to review EHR for eligibility. The team will request MCIT DataCore to generate a report identifying potential subjects that meet criteria and have upcoming office visit appointments. The study team, including principal investigator, co-investigators, and research assistants, will have access to the Epic search results and verify eligibility of potential subjects. The search results will include PHI- such as medical record numbers. Patients will then be contacted by phone, email, or MyChart portal using an IRB approved message or script. Subjects will also be approached during office visits to introduce the research project and be invited to participate in the study. In addition, the Clinical and Translational Science Institute (CTSI) Recruitment and Retention Core at NYU will be engaged to provide expert consultation.

Interested and eligible participants that have an upcoming clinic appointment will be met at the visit for consent and enrollment. If no clinic visits are upcoming, participants will be invited for a research only

visit. Participants will meet with a research coordinator to review eligibility and provide informed consent. Informed consent will include specific language regarding laboratory testing for the Olink biomarker panel and a separate consent subsection for participation in providing samples for future research. Study discussion and consenting will occur following a clinic visit in a secure private location in either the outpatient clinics or Clinical and Translational Research Institute of NYU Medical Center. Participant will be randomized to true or sham arm of the trial and baseline blood draw will occur at this clinic visit. Blood will be collected and stored for analysis. Participants will receive partial reimbursement for the initial blood draw, and the remainder of remuneration will be given at the final blood draw/equipment return.

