7.6 Final Study Visit

Final Study Visit (Visit 2: 4 weeks after PAC turned on)

- Participants return study equipment: PM monitors, BP monitor data hubs, electricity monitors
- Collect blood for post-intervention biomarker measurement: <15 mL for all, additional ~10 mL for participants opting into future research.
- Final blood draw must occur ≤35 days from turning on PAC

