7.7 Withdrawal Visit

Subjects may withdraw from the study at any time and visit will be scheduled to return any study equipment that has been received (PM monitors, BP monitor data hubs, electricity monitors). No withdrawal visit is required for withdrawal from future research.

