10.3 Statistical Methods

Aim 1 Analysis.

Descriptive summary statistics, such as mean and standard deviation (or median and inter quartile range) will be reported for continuous variables and counts and proportions for categorical variables. Graphical displays of all variables will be examined, with attention to assessing balance in these characteristics by intervention group, and with assessment of the distribution of variables, relevant to the choice of statistical tests. Statistical comparisons between the PAC and sham groups will be performed using a two-group two-sided t-test or nonparametric Wilcoxon test for continuous variables and Chi-square test for

categorical variables. Distributions of biomarker concentrations will be examined, and non-normally distributed concentrations will be log-transformed, as needed.

The analysis of our primary outcome will use linear mixed-effects models with the change in prespecified biomarker, from pre-intervention to post-intervention, concentrations as the dependent variable and treatment arm as the independent variable. While randomization should obviate the need for additional adjustment, models will be adjusted for age, gender and BMI, as these are known to be related to inflammatory biomarker concentrations.^{20, 21} These models use subject-specific random intercepts to account for heterogeneity between subjects and will account for within subject correlation between biomarker observations. The proposed model is:

$$\Delta TNF\alpha = \beta_1 + \beta_2(PAC\ arm) + \beta_3(age_i) + \beta_4(gender_i) + \beta_4(BMI_i) + e_i$$

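### The home blood pressure stopping rule in 5.2 can act only after randomisation, and nothing provides the final TNFα draw for those it stops

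*Combined protocol and SAP*

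**What the plan says.** Exclusion criterion 2 in section 5.2 covers "Participants with average home blood pressure monitor readings of a systolic blood pressure (SBP) >160 mmHg over any 10-day period during the study". It continues: "This will be considered evidence of uncontrolled hypertension and will require study termination". Since section 8 says the study as a whole has no predefined stopping rules, this is read here as ending that participant's participation.

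On timing, section 4.1 says "After enrollment and baseline blood draw, Home BP will be monitored", and section 5.4 says "Participant will be randomized to true or sham arm of the trial and baseline blood draw will occur at this clinic visit". Blood pressure at entry is handled separately, by inclusion criterion 4 (systolic below 160 mm Hg).

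On sampling, the instruction "Collect blood for post-intervention biomarker measurement" appears only under the Final Study Visit (7.6), four weeks after the air cleaner is switched on. For withdrawals, section 7.7 says a "visit will be scheduled to return any study equipment that has been received"; it mentions no blood. Section 5.7.2 records the date and reason and does not replace participants. Section 10.4 says non-completers contribute baseline-only data.

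On analysis, section 4.2.1 states "The primary study endpoint will be % change in concentration of" TNFα over the four weeks. Section 10.3 plans "linear mixed-effects models with the change in prespecified biomarker, from pre-intervention to post-intervention, concentrations as the dependent variable". Section 10.2 declares an Intention-to-Treat dataset.

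**The concern.** A rule that needs ten days of on-study home readings cannot screen anyone. It removes people who are already randomised, because of something that happens on treatment. That variable is not neutral between arms: section 2.1 reports a meta-analysis in which air cleaners lowered systolic pressure by about 4 mm Hg against sham. If that effect is real, somewhat more of the removals fall in the sham arm; if it is not, they split evenly.

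The blood draw would not otherwise be lost. It is already planned, and a participant with uncontrolled blood pressure can still give a sample. If the draw is skipped, that participant has no pre-to-post TNFα change, so the comparison called Intention-to-Treat leaves out randomised people selected on a post-randomisation variable. At stake are some precision and, in principle, some bias in a small trial.

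**Working it through.** **Step 1: when the rule can act.** Sections 5.4 and 4.1 give the order: randomisation and baseline draw at the same clinic visit, then home monitoring. Ten days of readings are needed, so the earliest trigger is about day 10 of monitoring. No one can meet the criterion before randomisation.

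**Step 2: what happens to the sample.** The four places that could provide a draw are 7.6 (Visit 2 only), 7.7 (equipment only), 5.7.2 (date and reason only) and 10.4 (baseline-only data expected). Sections 2.3.1 and 8 cover referral to the managing physician and safety review, not a research draw. That a stopped participant gives no final sample is an inference from this silence.

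**Step 3: what a baseline-only participant contributes.** With change as the dependent variable, nothing. Section 10.3 also mentions subject-level random intercepts. If pre and post values were modelled as separate rows, a baseline-only row would recover a fraction (1 − r)/2 of the lost information: 0.25 at an assumed pre-post correlation of r = 0.5, and 0.15 at r = 0.7.

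**Step 4: how many.** The documents give no SBP distribution, so every rate here is an assumption. Inputs: usual home SBP with mean 130–145 and SD 10–12; clinic measurement noise SD 10; entry below 160; day-to-day SD 8; 28 days of readings; trigger if any rolling 10-day mean exceeds 160. The air cleaner effect is either −4 mm Hg reached over 7 days, or zero. The trigger proportions come from simulation (150,000 per arm before the entry filter).

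With 22 per arm:
- Expected number at −4 = 22·p(sham) + 22·p(active); at zero effect = 44·p(sham).
- Standard-error ratio if every triggered draw is lost = √(1/n_s + 1/n_a) / √(2/22), where n_s and n_a are the numbers left in the sham and active arms.

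| Mean, SD | Sham % | Active % (−4) | Lost of 44 (−4 / zero) | SE increase % (−4 / zero) |
|---|---|---|---|---|
| 130, 10 | 0.22 | 0.05 | 0.06 / 0.10 | 0.07 / 0.11 |
| 135, 10 | 0.84 | 0.23 | 0.24 / 0.37 | 0.27 / 0.42 |
| 135, 12 | 1.71 | 0.65 | 0.52 / 0.75 | 0.60 / 0.87 |
| 140, 10 | 2.57 | 0.87 | 0.76 / 1.13 | 0.88 / 1.31 |
| 140, 12 | 3.90 | 1.62 | 1.21 / 1.71 | 1.42 / 2.01 |
| 145, 10 | 6.46 | 2.52 | 1.97 / 2.84 | 2.34 / 3.39 |
| 145, 12 | 8.01 | 3.68 | 2.57 / 3.53 | 3.09 / 4.26 |

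Check of the last row at −4: 22 × 0.0801 = 1.76 sham and 22 × 0.0368 = 0.81 active, total 2.57, sham excess 0.95. Remaining 20.24 and 21.19; √(1/20.24 + 1/21.19) = 0.311 against 0.3015, or +3.1%. At zero effect: √(22/20.24) = 1.043, or +4.3%.

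**Step 5: variants.**
- If only triggers reached by day 14 are acted on before Visit 2, the increase is 0.98–1.35% at (140, 12) and 3.0% at worst.
- Under the separate-rows reading, the worst case of 4.3% becomes 3.2% (r = 0.5) or 3.6% (r = 0.7).
- Sections 4.1 and 5.6 give 74 participants instead of 44. At 74 the range is 37 × (0.0022 + 0.0005) = 0.1 to 74 × 0.0801 = 5.9. The percentage increases are unchanged, because the proportions are the same.

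**Step 6: bias.** With a true TNFα effect of zero and an assumed correlation of 0.1–0.3 between usual SBP and TNFα change, the shift is 0.0005–0.018 SD. The standard error at 22 per arm is √(2/22) = 0.302 SD, so the largest shift is 0.018/0.302 = 6% of it.

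**The case against.** The strongest reply is that almost nothing follows from this. The largest simulated bias is about 6% of a standard error, and mid-range precision loss is 1.4–2.0%, in a pilot that already describes itself as budget-limited. That stands, and it makes the point minor. The upper figures may also be too high: the simulation treats every trigger as a lost draw, 28–43% of sham triggers come after day 14, and it ignores referral to the managing physician, which could lower pressure before a 10-day mean passes 160.

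A second reply is that the criterion's own wording shows it is an on-study rule, so its place in 5.2 is only editorial. That also stands; moving it between sections changes nothing for a participant.

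A third reply is that the lost draw is inferred. Section 7.7 opens with participant-initiated withdrawal, section 7.6 does not limit the draw to completers, and where the plan means to discard data it says so (5.7.1, for those who sleep away from home). A reader might therefore infer that the plan forbids a final sample or drops these participants from the analysis. No sentence does either. However, 5.7.2 treats withdrawal and termination together and 10.4 anticipates baseline-only data, so a missing sample remains the likeliest outcome of following the text.

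It is also tempting to say the 10% dropout allowance in 10.4 already covers the loss. It does not: the allowance fits 66/0.9 = 73.3, rounded up to the 74 in 4.1 and 5.6. The 44 is a budget figure, and section 5.4 randomises 44 to obtain 44 completers.

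**Conclusion.** The point holds as a minor one. Criterion 2 acts only after randomisation, through a variable the intervention is expected to change, and no section provides a post-intervention TNFα draw for those it stops. Followed as written, they would most likely have no value on the primary change endpoint.

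Under the assumed SBP distributions this concerns about 0.1–3.5 of 44 participants, with a standard-error increase of at most about 4%. The structural part needs no assumptions; the size rests entirely on them.

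A reader might infer that the rule biases the TNFα result materially, or in a known direction. Neither is supported. With a positive SBP–TNFα correlation and more sham losses, the sham mean change is pulled down. That understates a true benefit, but it moves the estimate away from zero if there is no effect. A negative correlation reverses the shift, and with no blood pressure effect the losses balance. The documents fix none of these conditions.

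**What to change.** Keep the 160 mm Hg threshold and the clinical referral. State in 5.7.1 and 7.7 that a participant who triggers the rule:

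- stays in the Intention-to-Treat set and keeps blood pressure data recorded up to the trigger;
- is asked for the planned 4-week draw, staying on the assigned device and blinded until then;
- returns equipment, and receives a HEPA filter if in the sham arm, only after that draw. Sections 4.1, 6.1 and 10.5.1 tie filter hand-over and unblinding to the final visit or equipment return, so an early return could put a sham participant on active filtration before the sample.

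If the participant will not continue, take the post-intervention sample at the equipment-return visit, before any filter is handed over. Report triggers by arm and day, and record blood pressure treatment changes. Listing the rule under 5.7.1 instead of 5.2 would be tidier.

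Cost: a wording amendment. There are no added participants, and the draws concerned (roughly 0–4 at 44 enrolled, 0–6 at 74) are already planned. Downside: blood pressure treatment changed after the trigger may add noise to the TNFα change and could differ by arm, which is why it should be recorded.
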